10.5 Interim-analysis

After enrolment of 100 patients, an interim-analysis will be performed with the following purposes:

1. To verify the relapse rate in the two treatment arms and stop the trial if more relapses have occurred in the low dose arm;
2. To check the relapse rate and re-do the power calculations if the rate significantly differs from that used to calculate the sample size when planning the study.

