3.6 Baseline and follow-up visits

At the baseline visit (Visit 1), each patient with newly diagnosed epilepsy will be screened for eligibility. Patients satisfying all the selection criteria will be informed of the study aims and asked to release a written informed consent. All the baseline data will be collected in an electronic case report form (e-CRF) and the patient will be then randomized. Follow-up visits will be scheduled at the discretion of the caring physician but telephone contacts will be programmed at 4 weeks, 3, 6, 9 and a clinic on-site visit at 12 months. An interval of \pm 1 week for the visit schedule is permitted. During each contact/visit the patient will be asked to report any seizure recurrence, adverse event and any additional information deemed important for the management of the disease. Patients will be invited to read the diaries and verify if any missing or incomplete information was present.

4. Study duration

Study duration: 36 months as indicated below:

- Administrative and ethical procedures: 6 months.
- Duration of patient enrolment: 12 months.
- Follow-up period: 12 months from the date of randomization.
- Database lock and statistical analysis: 30th-35th month.
- Final report and data publication: 36th month.
- Planned start of enrolment: as soon as the Ethics committee approval and signed contract are in house.

The end of study is considered the last patient last visit (LPLV).

5. Study population

Total number of patients: 374 considering 10% of expected dropouts.

Number of patients for each treatment arm = 168 (see Sample Size calculation for details).

6. Drug choice, tapering and maintenance daily dosages

The choice of the drug is left to the caring physician's discretion but it must be limited to the AEDs marketed for monotherapy use. All the study drugs will be used according to the respective SPCs, which will be sent by the promoter to all the study investigators.

For each individual drug, the following doses (in mg/day) have been selected as low vs. standard: carbamazepine, 300 vs 600; levetiracetam, 500 vs. 1000; valproate, 300 vs. 600; zonisamide, 150-300; oxcarbazepine, 600 vs. 1200; topiramate, 100 vs. 200; lamotrigine, 100 vs. 200; gabapentin, 450 vs. 900, lacosamide 100 vs. 200. Tapering to the assigned target dose will be performed as in

clinical practice but instructions will be imparted for each drug at the beginning of the study.

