8.7 Data Monitoring Committee (DMC)

According to the EMEA GUIDELINE ON DATA MONITORING COMMITTEES (January 2006) a Data Monitoring Committee (DMC) is an external group of independent experts assessing the progress, safety data and efficacy endpoints of this clinical study. In order to do so, a DMC may review study information (on a patient level or treatment group level) during the conduct of the study. Based on its review, the DMC provides the Principal Investigator with recommendations regarding study modification, continuation or termination. Safety monitoring will be the major task for a DMC. The DMC might need access to efficacy information to perform a risk/benefit assessment in order to weigh possible safety disadvantages against a possible gain in efficacy.

Based on the results of the monitoring activities, the DMC is expected to consider recommendations about stopping the trial for efficacy and/or safety and/or for sample size adjustment without violating the concepts behind the original study protocol.

If changes in the study conduct are recommended by a DMC, sufficient information should be provided to allow the Principal Investigator to decide whether and how to implement these recommendations. The implementation of any DMC recommendation is solely the responsibility of the Principal Investigator who is also free to neglect (in whole or in part) recommendations of a DMC.

The DMC has to be fully functional before enrolment into the study starts to enable it to respond to any safety signal.

As DMC work is a multidisciplinary task, the DMC needs expertise from different scientific areas. The member of the DMC will include a biostatistician, a member of an ethical committee, a neurologist and a pharmacovigilance expert.

All members of the DMC will be qualified persons, they should also have practical experience with conducting clinical trials, a good understanding of the problems and limitations of clinical trials, have no financial interest in the outcome of the study.

The DMC will meet after the enrollment of at least 25% of patients and after three months of study.

The following DMC meeting will take place after the enrollment of 50% of patients.

9. Resource utilization

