10.4 Outcome measures, statistical methods and data analysis

Expected outcomes are the following:

1. compared to patients assigned to standard daily doses, patients receiving low daily doses of AEDs are expected to incur in similar rates of seizure recurrence;
2. compared to patients assigned to standard daily doses, patients receiving low daily doses of AEDs are expected to undergo significantly less treatment changes due to intolerable drug-related adverse events;
3. compared to patients assigned to standard daily doses, patients receiving low daily doses of AEDs are expected to experience less drug-related intolerable adverse events;
4. compared to patients assigned to standard daily doses, patients receiving low daily doses of AEDs are expected to experience a better quality of life;
5. the National Health System is expected to incur in significant savings with low daily doses of AEDs.

Primary outcome

The proportion of patients experiencing a treatment failure motivated by the need to change the assigned dose or the assigned drug for seizure relapse during the follow-up.

Secondary outcomes

1. the proportion of patients experiencing a treatment failure motivated by intolerable drug-related adverse events during the follow-up;
2. QOLIE-31 total score at the last visit;
3. the score of the seven PSQ-18 subscales (general satisfaction, technical quality, interpersonal manner, communication, financial aspects, time spent with doctor, accessibility and convenience) at the last visit;
4. the mean daily patient's cost of health care resources consumed for the management of epilepsy during the first 12 months of the study.

Descriptive statistics will be provided for all the data collected at admission, comparing the two

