10.6 Sample size calculation

The sample size is based on the primary efficacy end-point. The non-inferiority margin is a relative 20% difference, as stipulated by the ILAE, up to a maximum of an absolute 15% difference between the two dosing schedules for the primary endpoint. Assuming a one-sided p of 0.025 and that the proportion of patients who will not have a seizure in the low dose and standard dose groups is 60%, 168 patients per group provides 80% power to test whether a low AED dose is non-inferior

to a standard dose. Assuming 10% drop-out rate, the required sample size will be 374 patients.

11 Administrative procedures

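### Interim item 1 in section 10.5 stops the trial on any numerical excess of low-dose relapses, with no threshold, test or data cut and no link to section 8.7; applied literally and as binding, it would cut the stated 80% power to roughly 48-53%

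*Combined protocol and SAP*

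**What the plan says.** Section 10.5 sets the look by enrolment only: "After enrolment of 100 patients, an interim-analysis will be performed with the following purposes". Item 1 is to check relapse in each arm and "stop the trial if more relapses have occurred in the low dose arm". Item 2 is to redo the power calculation, but only if the relapse rate departs significantly from the planning value. Item 1 has no such qualifier.

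Section 10.6 assumes 60% seizure-free in both arms and a one-sided 0.025 test, and states that "168 patients per group provides 80% power". The margin is a relative 20%, "up to a maximum of an absolute 15% difference between the two dosing schedules". No allowance is made for an interim stop. Section 10.4 states the expectation that "patients receiving low daily doses of AEDs are expected to incur in similar rates of seizure recurrence".

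Section 8.7 has the DMC "consider recommendations about stopping the trial for efficacy and/or safety and/or for sample size adjustment". Acting on its advice is "solely the responsibility of the Principal Investigator who is also free to neglect (in whole or in part) recommendations of a DMC". Section 8.7 gives no threshold and does not mention the 100-patient look, and 10.5 does not mention the DMC.

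**The concern.** When the arms are truly equal, which arm has more relapses at an early look is close to a coin toss, apart from ties. A rule that stops on an excess of one therefore works against a design whose purpose is to show that any deficit is smaller than a margin. It would end many trials in which the planning assumption is correct, and the 80% in 10.6 would not describe the plan as written.

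The status of the rule is also open. Item 1 can be taken as a binding instruction or as shorthand for a safety purpose handled under 8.7. On either reading, whoever applies it has no threshold and no data cut, so two competent readers could act differently on the same data.

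**Working it through.** **Inputs from the documents.** Relapse 40% in each arm (1 − 0.60), one-sided alpha 0.025, 168 per arm, 10% drop-out (10.6); 1:1 allocation (3.4), so about 50 per arm at the 100-patient look; 12 months of follow-up (3.5); enrolment over 12 months (section 4).

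**Step 1: reproduce the plan's figure.** n per arm = (1.960 + 0.842)² × 2 × 0.60 × 0.40 / 0.15² = 7.849 × 0.48 / 0.0225 = 167.4, so 168. With drop-out, 168 / 0.9 = 186.7, so 187 per arm and 374 in total. Power at 168 = Φ(0.15/√(0.48/168) − 1.960) = Φ(0.846) = 0.80. This works only with a 15-point margin. A relative 20% of 60% is 12 points, at which 168 per arm gives about 61% power. That is a separate matter; 15 points is used below because it is the value behind the stated 80%.

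**Step 2: stop probability with equal arms.** Let f be the share of eventual relapses already seen at the cut. Interim relapses in each arm are Bin(50, 0.40f), so 20f are expected per arm. The literal rule stops if X_low > X_std; ties continue. P(stop) = Σ P(X_low = x) P(X_std < x) = (1 − P(tie))/2.

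**Step 3: power with a binding stop.** Power is the probability that X_low ≤ X_std at the look and that the upper limit of the final unpooled Wald 95% CI for the difference (168 per arm, interim patients included) is below 0.15. Exact calculation:

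| Expected relapses per arm at the cut | P(tie) | P(stop) | Power | Ceiling 1 − P(stop) |
|---|---|---|---|---|
| 0.5 | 0.465 | 0.267 | 0.593 | 0.733 |
| 1 | 0.309 | 0.345 | 0.534 | 0.655 |
| 2 | 0.210 | 0.395 | 0.499 | 0.605 |
| 3.2 | 0.165 | 0.417 | 0.486 | 0.583 |
| 5 | 0.134 | 0.433 | 0.479 | 0.567 |
| 10 | 0.100 | 0.450 | 0.478 | 0.550 |
| 20 (all 100 followed for 12 months) | 0.081 | 0.459 | 0.496 | 0.541 |
| no interim stop | – | – | 0.800 | – |

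**Step 4: which row is plausible?** The documents do not say. Assume even accrual of 374 over 12 months and a constant hazard (neither is in the documents). The 100th patient then enrols at 12 × 100/374 = 3.2 months. The hazard is −ln(0.60)/12 = 0.0426 per month, and the average risk accrued by then is about 6.5%, or 3.3 relapses per arm. A cut at that moment gives about 42% stopping and 49% power.

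**Step 5: a larger sample.** Power cannot exceed 1 − P(stop). In every row this ceiling is below 0.80, so the re-calculation under item 2 cannot restore 80% while the literal stop stays in force.

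**Step 6: what triggers the false stops.** At 3.2 relapses per arm, 64% of stops with equal arms come from an excess of only 1 or 2 relapses. At full follow-up, 86% come from an excess of 7 or fewer out of 50 (under 15 points), and 72% from 5 or fewer (under 12 points).

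**Step 7: type I error of item 1.** At a true 15-point deficit (55% against 40%) and fixed n, the chance of a false non-inferiority claim is 2.6% without the stop and 1.1-1.6% with it, for 1 to 20 relapses per arm. A stop of this kind can only remove claims.

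**The case against.** The strongest reply is that item 1 was never meant to bind. Section 10.5 lists purposes, not decision rules. Section 8.7 gives the DMC the same two topics, stopping and sample-size adjustment, includes a biostatistician, and sets a first meeting at no less than 25% of patients (0.25 × 374, about 94) and after three months. That is close to the 100-patient look. The Principal Investigator may then set the advice aside. This is a fair reading, and it means a reader should not infer that the plan has no decision chain at all: 8.7 supplies a general one. What it does not supply is a threshold or a data cut, and neither section points to the other. The gap remains.

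A second reply is that stopping readily is a deliberate safeguard when patients receive lower doses. That may be so: at a true 15-point deficit with full follow-up, the current rule stops 92% of trials. But a deliberate trade needs its price stated, and 10.6 states 80% as if there were none.

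A third reply concerns the numbers. A reader might infer that the trial's power simply is 48-50%. The documents do not support that: the figure requires binding use, and it moves with an undefined data cut (59% at 0.5 expected relapses per arm). The full-follow-up row would fall at about month 15 on the accrual assumed here, after enrolment has closed, so it is an extreme case. A reader might also infer that the interim inflates type I error. Item 1 alone, with fixed sample size, does not; item 2's re-calculation was not assessed here.

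**Conclusion.** The concern holds as a defect in the wording of 10.5 item 1 and its missing link to 8.7. The criterion as written is any numerical excess, which contradicts a non-inferiority design that assumes equal relapse and accepts a bounded deficit (relative 20%, capped at 15 points).

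The power loss is conditional. If the rule is literal and binding, with 50 per arm at the look and a 15-point margin, it stops about 35-46% of trials with equal true rates when 1 to 20 relapses per arm are expected, and power is about 48-53% against the stated 80%. If the rule is advisory, the true loss lies somewhere between zero and these figures, and nobody can say where, because the stop probability is undefined. The arithmetic is firm. Which reading applies is for the sponsor to state.

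**What to change.** In 10.5, replace the bare excess with a pre-specified statistical boundary for excess low-dose relapse, applied at a stated number of relapses or amount of follow-up. The sponsor and DMC choose the threshold. State whether the boundary is binding and who applies it, and reconcile and cross-reference 10.5 and 8.7.

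In 10.6, report the sponsor's own stop probability with equal arms, the stop probability at a margin-sized deficit, and the resulting power. If the present rule is kept as binding, the 80% must be restated for the chosen data cut.

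The drafting cost is a paragraph in 10.5, a sentence or two in 10.6 and an entry in the DMC charter. The real cost is protection: a stricter boundary less often stops a truly inferior low dose early. As an illustration only, simulated under the Step 4 accrual and hazard assumptions with a cut at the 100th enrolment, the current rule stops about 42% of trials with equal arms and 67% at a 15-point deficit, with power 0.49. A one-sided log-rank boundary at p<0.20 gives about 21%, 42% and 0.65, and one at p<0.10 about 11%, 26% and 0.72. Both error rates should be in view when the threshold and the data cut are chosen.

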10.6 Sample size calculation

The sample size is based on the primary efficacy end-point. The non-inferiority margin is a relative 20% difference, as stipulated by the ILAE, up to a maximum of an absolute 15% difference between the two dosing schedules for the primary endpoint. Assuming a one-sided p of 0.025 and that the proportion of patients who will not have a seizure in the low dose and standard dose groups is 60%, 168 patients per group provides 80% power to test whether a low AED dose is non-inferior

to a standard dose. Assuming 10% drop-out rate, the required sample size will be 374 patients.

11 Administrative procedures

11.1 Regulatory and ethical compliance

This clinical study was designed and shall be implemented and reported in accordance with the protocol, the ICH Harmonized Tripartite Guidelines for Good Clinical Practice, with applicable local regulations and with the ethical principles laid down in the Declaration of Helsinki.

11.2 Responsibilities of the investigator and IRB/IEC/REB

The protocol and the purposed informed consent must be reviewed and approved by a properly constituted IRB/IEC/REB before study start.

Prior to study start, the investigator is required to sign a protocol signature page confirming his/her agreement to conduct the study in accordance with these documents and all of the instructions and procedures found in this protocol and to give access to all relevant data and records to monitors.

11.3 Informed consent form and Informed consent procedures

Eligible patients may be included in the study after proving written IRB/IEC/REB-approved informed consent, or, if incapable of doing so, after such consent has been provided by a legally acceptable representative of the patient.

11.4 Amendments to the protocol

Any change or addition to the protocol can only be made in a written protocol amendment.

Only amendments that are required for patient safety may be implemented prior to IRB/IEC/REB approval in according to the Italian legislation. Notwithstanding the need for approval of formal protocol amendments, the investigator is expected to take any immediate action required for the safety of any patient included in this study, even if this action represents a deviation from the protocol.

In according with the GCP rules and the Italian legislation, the acceptance of an amendment of the study protocol by each participating institution is subjected to the local IRB/IEC/REB approval.

11.5 Insurance

In keeping with the Italian law, the trial will receive an insurance coverage (DM 213, July 14 2009).

| Neurological examination | X | | | | | X | X | X | X | X |
| Psychiatric examination | X | | | | | | | | | |
| Concomitant diseases | X | X | X | X | X | X | X | X | X | X |
| Concomitant treatments | X | X | X | X | X | X | X | X | X | X |
| Birth control | X | X | X | X | X | X | X | X | X | X |
| Epilepsy history | X | | | | | | | | | |

| | | | | | | | | | | |
|--|---|---|---|---|---|---|---|---|---|---|
| QOLIE 31 and PSQ-18 inventories | X | | | | | X | | | | |
| First interictal EEG | X | | | | | | | | | |
| Results of follow-up interictal EEG (if performed) | | X | X | X | X | X | X | X | X | X |
| Imaging (CT, MRI) findings | X | | | | | | | | | |
| AED plasma concentration and other biochemical/hematological parameters (if performed) | X | X | X | X | X | X | X | X | X | X |
| Randomization | X | | | | | | | | | |
| Assessment of seizures, AE/SAE | | X | X | X | X | X | X | X | X | X |
| Assessment of contacts with the NHS | | X | X | X | X | X | X | X | X | X |
| Delivery of patient's diary | X | | | | | | | | | |
| Assessment of patient's diary data | | X | X | X | X | X | X | X | X | X |
| Return of patient's diary | | | | | | X | | | | |
| Assessment of compliance | | X | X | X | X | X | X | X | X | X |

| | | | | | | | | | | |
|-----------------------------|---|---|---|---|---|---|---|---|---|---|
| Next contact/visit schedule | X | X | X | X | X | | X | X | X | X |
| Final questions | | | | | | X | | | | |

*Visit at 4 weeks, 3, 6 and 9 months will be performed by phone (TC). The other visits will be performed as clinic on-site visits.

PROTOCOL APPROVAL PAGE Version 3.0 December, 20 2021

[name]**Date**

Istituto di Ricerche Farmacologiche Mario Negri IRCCS
Milano, Italy

I have read the Protocol Final Version 3.0 Dec, 20 2021. I agree to conduct this study as outlined herein.

Investigator Name

Investigator Institution

Investigator Signature**Date**
